7.2 Study Procedures

7.2.1 Part 1

On or before the date scheduled for Study 1, a member of the research team who is not part of the ALS clinical team will describe the procedures and receive written informed consent from the patient and caregiver dyad, as well as the respiratory therapist. The participant team undergoes the initial in-person pulmonary function testing, followed 2-3 hours later at the end of the clinical visit by the rPFT. rPFT administration is described in Section 7.4.2. For roughly half of the enrolled participants, the order of assessments is reversed. Following the study procedures, the therapist and patient/caregiver dyad will complete a survey concerning the ease of use and confidence in the rPFT assessment.

Part 1 includes the recruitment of up to 20 practice control participants for validation of the study procedures. They will perform the same procedures as the patient and caregiver, in conjunction with the respiratory therapist.

7.2.2 Part 2

Following consent, the researcher will collect demographic and clinical information: date of birth, gender, time since symptom onset, ALSF Functional Rating Scale - Revised, PFT history, and region of symptom onset. The researcher will guide the subject through completion of the respiratory health questionnaire and self-efficacy assessment.

Subjects consented on the day of their in-person clinic visit will be sent home with an rPFT kit and scheduled for weekly training appointments with a member of the research team. For patients consented remotely, the research team will ship a kit and schedule them for weekly training appointments.

The weekly schedule following the first site visit at week 0 is shown in **Error! Reference source not found.** Weekly training sessions will be guided through the telehealth interface by a member of the research team. If by the 4th training session the participant is able to complete rPFT procedures without guidance as determined by the researcher-completed aptitude assessment, and achieve an FVC result within 10% of the average value from the first three sessions, the participants will be randomized to one of the two study arms.

Patients may be enrolled without a caregiver available if the investigator determines that the patient is able to perform the home breathing tests without additional assistance. The patient's ability to perform these tests solo will be reviewed at a minimum interval of successive clinic visits. If they are no longer able to perform the home tests without additional assistance, a caregiver must be enrolled aid home PFT administration, or they will be exited from the rPFT portion of the study. Caregivers enrolled part-way into the study will receive training on administering rPFTs at that time.

rPFT arm: Subjects will continue to self-administer rPFTs every week. A research team member will schedule rPFT training appointments at weeks 8 and 12 order to re-assess aptitude. rPFT procedures are not performed during weeks in which a clinical appointment occurs. Subjects will complete the following patient-reported outcomes:

- Respiratory health questionnaire (monthly) - The questionnaire contains three Patient-Reported Outcomes Measurement Information System (PROMIS) sub-scales on Dyspnea Characteristics (5 items, [PROdc2016]), Dyspnea Functional Limitations (10 items, [PROdfi2016]), and Sleep Related Impairment (8 items, [PROsri2016]). The PROMIS sub-scales, all of which utilize Likert-type scaling, will be summed as composite scores, with higher numbers indicating poorer quality of life. Also included are seven questions regarding respiratory complications experienced in the previous month.
- Self-efficacy assessment (quarterly) - The self-efficacy assessment contains questions from the PROMIS item banks on Self-Efficacy for Managing Symptoms (9 items, [PROms2017]), Self-Efficacy for Managing Social Interactions (5 items, [PROsi2017]), and Self-Efficacy for Managing Medications and Treatments (4 items, [PROmt2017]). These assessment tools, designed for use in chronic conditions, are scored as an average of individual components on a 1-5 scale.
- ALS-Specific Quality of Life (quarterly) – Brief Form [Felgoise2018] – 20 questions in 5 domains encompassing quality of life. If the subject has completed this document in the last 30 days as part of clinical care, we may access this data from their chart.

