1.0 Objectives

1.1 Study Objectives

The specific objective of this proposal is to utilize the practice of telemedicine via connected health devices to enable the guided performance of a remote pulmonary function test (rPFT) in the home. The rationale for this study is to determine whether telemonitoring of respiratory health can help exceed standards of ALS care.

Part 1: Demonstrate the reliability of remote pulmonary function testing, performed via telemedicine, for monitoring respiratory function in patients with amyotrophic lateral sclerosis (ALS)

Primary Hypothesis: There is no difference in the results of PFT and rPFT for respiratory assessment of FVC and MIP.

Secondary Hypothesis: The respiratory therapist, patient, and caregiver will express confidence in conducting the rPFT, as determined by surveys of procedure acceptance.

Part 2: Weekly remote pulmonary function testing (rPFT) and nurse respiratory health coaching (NRHC) in ALS telemedicine

This part randomizes subjects into two arms – both perform weekly rPFT testing and one receives monthly NRHC.

Aim 1: Clinically-meaningful benefit of weekly rPFT

Primary Hypothesis: Home respiratory assessment enables thresholds for non-invasive ventilation (NIV) recommendation to be met on average 30 days sooner when measured weekly compared to the standard 3-month interval.

Secondary Hypothesis: Determine the factors associated with adherence to weekly rPFT procedures.

Aim 2: The impact of NRHC on patient outcomes

Primary Hypothesis: Patient and caregiver teams in the NRHC arm report higher self-efficacy in the respiratory management of the disease at 6 months compared to those in the non-NRHC arm.

Secondary Hypotheses: Patients in the NRHC arm report higher self-efficacy at 12 months, experience less decline of respiratory-related quality of life and fewer respiratory complications compared to those in the non-NRHC arm.

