2.2 Previous Data

Preliminary work by our group as part of a pilot study assessing the benefits of ALS telemedicine has shown that the practice of live telemedicine is viewed favorably by ALS patients, caregivers, and multidisciplinary ALS team members, although less so by the latter group (Figure 1, [Morris2016, Geronimo2017]). Overall, the three rater groups were concerned that the lack of physical contact lessened the ability for providers to deliver equal care. This led us to identify and act upon one area of care that could be improved in telemedicine – assessment of breathing function.

[figure not shown]

Figure 1: Patient (P), caregiver (C), and health care provider (H) ratings of the ALS telemedicine pilot in four domains [Geronimo2017]. Circles containing an X mark the medians, thick lines span the first to third quartile of data, with thin lines extending up to two times this range. Outliers are those small circles outside this range

From January to September 2018, the procedures for part 1 were completed in forty patients. The main result was that the simulated remote assessment produced similar values of FVC and MIP compared to standard assessments (Figure 2). In this sample, the specificity and sensitivity of FVC measurements were 100%, for MIP assessments was 89% and 82%, respectively [Geronimo2019]. The results of part 1 indicate that rPFTs are accurate and acceptable measures of respiratory health.

[figure not shown]

Figure 2: FVC (Left) and MIP (Right) data from 40 subjects of the rPFT pilot study, comparing standard PFT measures to therapist-guided remote assessments. Four shaded quadrants are created by segmenting standard and remote tests by predefined clinical thresholds.

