7.0 Study Design and Procedures

7.1 Study Design

Part 1: This is a self-controlled study where each participant will be administered a standard of care PFT for measurement of FVC and MIP, as well as an rPFT, separated by at least an hour, for measurement of

experimental FVC and MIP. The rPFT is guided by a respiratory therapist in another room, utilizing the telemedicine interface of the Hersey ALS clinic and devices for measuring FVC and MIP (**Error! Reference source not found.**).

[figure not shown]

Figure 3: Tools for remote pulmonary testing. Left: Air Smart Spirometer and turbine. Right: respiratory pressure meter and mouthpiece.

Part 2: This is a two-arm, randomized study to determine 1) whether weekly monitoring of respiratory function can lead to timelier initiation of NIV and 2) whether structured nurse coaching leads to improved self-efficacy for managing disease and better maintenance of respiratory health. For enrollees in both arms, standard FVC and MIP measurements obtained approximately every three months by the respiratory therapist during ALS Clinic are supplemented with self-administered rPFTs performed weekly. To train the participant in the performance of rPFTs, a member of the research team will be present either in person or virtually to guide the patient and caregiver in the appropriate use of the equipment during the first four weeks of the study. Enrollees in the NRHC arm will additionally receive monthly coaching with the study nurse via telehealth. Approximately 5% of NRHC sessions will include audio recordings that will be evaluated by a second clinician nurse for quality and consistency.

rPFT protocol

Two devices are used to measure respiratory function:

- 1) Air Smart Spirometer, NuvoAir AB

The following information is paraphrased from the user manual, which is included in the “devices” page of the protocol.

The Air Smart Spirometer measures the forced vital capacity (FVC) in a forced expiratory maneuver. The Air Smart Spirometer is intended to be used by:

- Healthcare professionals trained to perform spirometry tests on patients.
- Adults trained by healthcare professionals or through self-learning who understand how to perform a high quality spirometry test.

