During each guided rPFT administration, a member of the research team and/or respiratory therapist will guide the patient and caregiver through three valid maneuvers of the FVC and MIP tests. The participants prepare the spirometer by connecting it to the tablet and opening the associated application. The patient is told to sit as upright as possible for the measurement of FVC. They will be told that to do this they will 1) inhale maximally, 2) exhale as hard and fast as possible, and 3) continue to exhale until indicated by the therapist. The researcher will also demonstrate this procedure to the patient. The caregiver applies nose clips to block airflow through the nose, holds the turbine of the spirometer to the patient's mouth and performs three repetitions of this sequence, with periods of relaxation between testings. Testing is repeated until three valid maneuvers are achieved. The application on the tablet computes the FVC and percentage predicted value, the best of which is retained.

To perform the MIP test, the participant inserts the mouthpiece into the pressure meter. The patient is told they will be asked to draw breath in as quickly and powerfully as possible, for at least one second. The researcher tells the caregiver to place a finger over the valve outlet so that no air flows through the mouthpiece during inhalation. Nose clips will be used. The patient performs three repetitions of this task. The maximal negative pressure from a valid run is recorded.

Each piece of reusable equipment will be labeled with an identification number. A log of all loaned materials will be maintained by the researchers. This log, included in the supporting documents, will be maintained on REDCap. Before delivery of the system to the study participant, each piece of equipment will be inspected and tested. This study will not collect prior medical therapy relevant to the use of the device. There are no restrictions on medicines or therapies used by the participants in this study.

Randomization (Part 2 only)

An unblinded blocked minimization method will randomize participants based on demonstrated factors affecting prognosis [Chio2009]. These include: time since diagnosis, age at consent, most recent FVC, and FVC slope from up to the previous year, if available.

NRHC protocol (Part 2 only)

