8.0 Subject Numbers and Statistical Plan

8.1 Number of Subjects

Approximately (but no more than) 123. We will enroll **40 patient/caregiver teams for Part 1** and up to **60 patient/caregiver teams for Part 2** to achieve 40 pairs completing procedures for Part 2.

Participants in the two studies may overlap. Up to **20 practice control participants** may be recruited for Part 1. Up to **three respiratory therapists** will also be recruited for these studies.

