8.3 Statistical methods

Part 1: The primary hypothesis is that there is no difference in the results of PFT and rPFT for respiratory assessment of FVC and MIP. We will use a paired sample t-test to determine if the mean test results are comparable between the standard and experimental treatments. We will conduct a qualitative analysis to determine whether the patient, caregiver, and therapist determine the rPFT to be an effective way to conduct tests of breathing function.

Part 2: Aim 1 will be analyzed to determine if the study date of NIV initiation is at least 30 days sooner based on rPFTs compared to standard clinic PFTs. This will be done using a non-parametric two sample test of means, the Wilcoxon-Mann-Whitney rank sum test. For analysis of Aim 2, a linear mixed effects model will be used to analyze the change from baseline between study groups of self-efficacy scores and respiratory health [Verbeke2000]. The effect size will be quantified from the model using the difference in means between the groups with their associated 95% confidence intervals.

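### Part 1 reverses the test order in roughly half of the patients, but the planned paired t-test ignores order; an order term would be a cheap, small improvement

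*Combined protocol and SAP*

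**What the plan says.** All references are to the combined protocol and SAP.

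- **Hypothesis (1.1):** "There is no difference in the results of PFT and rPFT for respiratory assessment of FVC and MIP". No margin is attached to it.
- **Order and timing (7.2.1):** the in-person PFT comes first, "followed 2-3 hours later at the end of the clinical visit by the rPFT". Then: "For roughly half of the enrolled participants, the order of assessments is reversed". Section 7.1 describes the two tests as "separated by at least an hour", which is compatible with the longer gap.
- **Assignment of order:** none is described. The randomization paragraph in 7.1 is limited by its heading to Part 2.
- **Analysis (8.3):** "We will use a paired sample t-test to determine if the mean test results are comparable between the standard and experimental treatments". Neither 8.3 nor any other section mentions an order or period term, stratification by order, or a check for an order effect.
- **Size and status:** section 8.1 plans "40 patient/caregiver teams for Part 1", and section 2.2 reports: "From January to September 2018, the procedures for part 1 were completed in forty patients". The order split is not reported.

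**The concern.** Reversing the order makes this a two-order paired design, and there is little reason to reverse unless order might matter. Both tests need repeated maximal efforts, so some average change between sessions, from fatigue or practice, is plausible.

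A t-test that pools the two orders does not separate that change from the difference between methods. In patients who have rPFT second the change is added to rPFT minus PFT; in the others it is subtracted. The opposite signs widen the spread of the differences. They cancel in the mean only if the two groups are equal in size, which an approximate half does not guarantee.

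The direction matters because Part 1 sets out to show no difference and has no margin. A non-significant result is likely to be read as comparability, so at an even split a needlessly large standard error helps the study's own hypothesis.

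**Working it through.** **Inputs.** n = 40 pairs (8.1, 2.2). The documents give no SD, order effect, split, alpha or power for Part 1, so there is no stated figure to reproduce. Assumed: two-sided alpha of 0.05; average first-to-second change π of 0.1, 0.25 or 0.5 σ, where σ is the within-order SD of the differences; splits from 20:20 to 28:12.

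**Model.** For one patient, d = rPFT − PFT = τ + sπ + e. Here τ is the method difference, s = +1 if rPFT is second and −1 if it is first, and e has SD σ. Let n1 patients have rPFT second and n2 have it first.

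**Plain paired t-test.**
- Expected mean of d = τ + π(n1 − n2)/n.
- Expected sample variance of d = σ² + π² × (4·n1·n2/n²) × n/(n − 1).

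At 20:20 with π = 0.5σ, the variance is 1 + 0.25 × 40/39 = 1.256 σ². The SD, and so the standard error, is inflated by √1.256 = 1.121. At 24:16 the bias is π × 8/40 = 0.20π.

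**Order-adjusted estimate.** Take the average of the two within-order means, with SE = (σ/2)√(1/n1 + 1/n2) on n − 2 degrees of freedom. This gives 0.158σ at 20:20, 0.159σ at 22:18 and 0.161σ at 24:16, whatever the value of π.

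| π/σ | Plain SE at 20:20 (σ) | Rise in SE | Bias at 22:18 (σ) | Bias at 24:16 (σ) |
|---|---|---|---|---|
| 0.1 | 0.159 | 0.5% | 0.010 | 0.02 |
| 0.25 | 0.163 | 3.2% | 0.025 | 0.05 |
| 0.5 | 0.177 | 12.1% | 0.050 | 0.10 |

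**Test behaviour** (simulation, 50,000 samples per setting).
- *Even split.* The plain test has type I error of 4.3% at π = 0.25σ and 3.0% at 0.5σ. Power for a true difference of 0.45σ (an illustrative value) falls from about 79% to 77.5% and 71.8%. With an order term it stays at about 79%.
- *Uneven split.* The bias works against the conservatism. At π = 0.5σ the plain test's type I error is 6.2% at 24:16 and 17.8% at 28:12, against about 4.9% with an order term.

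So the test is conservative at an even split, but not once the split is clearly uneven.

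**The case against.** **The effect may be negligible.** Counterbalancing is itself a protection against order effects. The procedures also limit fatigue and learning: the manoeuvre is demonstrated, there is rest between efforts, and the best result is kept. At 22:18 with a shift of 0.1σ, the bias is 0.010σ and the two standard errors are practically equal. Nothing in the documents supports a shift as large as 0.5σ. This stands, and it keeps the point minor.

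**A larger weakness lies elsewhere.** Inferring comparability from a non-significant test without a margin is unsound with or without an order term. This also stands; the order term does not cure it.

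**Part 1 is finished.** A change to 8.3 alters no future data collection, and section 2.2 cites a published report that may already have examined order. That report is not available here. A re-analysis remains possible only if order was recorded.

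**Stronger readings that the documents do not support:**
- A reader might infer that the accuracy claim behind Part 2 is undermined. Section 2.2 also rests that claim on sensitivity and specificity at clinical thresholds, which an order term in the mean comparison would not change.
- A reader might infer that limits of agreement are too wide. Section 8.3 plans no analysis of the spread of differences.
- A reader might assume that order is on file for all 40 patients. No section says so.
- A reader might take the adjusted estimate as unbiased without condition. Order is not stated to be randomised, so this needs the method difference not to depend on which patients received which order.

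**Conclusion.** The point holds as a minor improvement to the analysis. The design reverses order and the stated test ignores it, so the average first-to-second change goes into the standard error and, with unequal groups, into the mean. That much is algebra.

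Its practical size is unknown. It depends on the assumed shift, within-order SD and split, none of which the documents give. With a shift of 0.25 SD or less and a near-even split, the standard error is about 3% too large at most and the bias about 0.025 SD at 22:18. The effect becomes material only if the shift is nearer 0.5 SD or the split is clearly uneven.

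Adjustment removes only the average order effect. Change that differs from patient to patient stays in the error.

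**What to change.** In 8.3, for FVC and MIP separately, estimate the rPFT − PFT difference as the average of the two within-order mean differences (a paired model with an order term). Take the confidence interval from that model. Report how many patients had each order and how order was assigned. If test order was recorded, re-analyse the completed Part 1 data in this way and report the estimated order effect. State the assumption that the method difference does not depend on which patients received which order.

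The cost is one degree of freedom and, if order is on file, a short re-analysis. If the order effect is negligible and the split uneven, the adjusted standard error is slightly larger: 0.161 against 0.158 SD at 24:16, or about 2% (0.161/0.158 = 1.02). No new data are needed.

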7.3 Duration of Participation

Part 1: The study procedures, including screening, consent, assessment, and survey, are expected to take 45 minutes. Administration of the simulated PFT with patient participants will be performed on the day of a scheduled clinic visit.

Part 2: Patient participants will be enrolled for approximately one year. During this time, patients will engage in approximately five standard PFT assessments during in-person or telehealth clinic activities, requiring no additional time commitment. Participants will also complete approximately 47 rPFTs, each taking 10-30 minutes to complete, depending on level of experience. The respiratory questionnaire and the self-efficacy assessment each take approximately 10 minutes to complete. Finally, those in the NRHC arm will receive up to 12-30 minute coaching sessions and 3-30 minute coaching checkups.

Patients receiving nurse coaching can expect a total time commitment of approximately 26.5 hours, and those in the non-coached group can expect 19 hours of time spent on study procedures. Caregivers may be enrolled for the same period or for a shorter period depending whether one is available and needed at the initiation of study procedures.

8.0 Subject Numbers and Statistical Plan

8.1 Number of Subjects

Approximately (but no more than) 123. We will enroll **40 patient/caregiver teams for Part 1** and up to **60 patient/caregiver teams for Part 2** to achieve 40 pairs completing procedures for Part 2.

Participants in the two studies may overlap. Up to **20 practice control participants** may be recruited for Part 1. Up to **three respiratory therapists** will also be recruited for these studies.

8.2 Sample size determination

Our sample size is predetermined based on our subjective ability to recruit patients within the time frame of the study. Power analysis was based on studies of FVC decline. Lo Coco et al., [LoCoco2006], showed that 50% of study participants dropped below 50% predicted FVC in one year. Given that our exclusion criteria for Part 2 will reject many of the 37% of individuals in their study who were “slow progressors,” we estimate that 75% of patients enrolled in our study will meet the respiratory criteria to recommend NIV. This results in a sample size per arm of n=15, which provides 80% power to detect a difference in mean outcome between the two groups if the effect size is found to be 0.95.

Assuming a monthly change in FVC of $3.5 \pm 3.4\%$ found by Schiffman et al. [Schiffman1993], we conducted 10,000 Monte-Carlo simulations of 40 participants declining at this rate for 12 months. Half were sampled once every three months, and half were sampled every month. $80.6 \pm 6.3\%$ of simulated participants met the requirements for NIV recommendation, in roughly equal proportions across groups. The average FVC at recommendation was 47.0% predicted in the experimental group, and 43.4% predicted in the control group. The effect size of the difference in FVC between groups was $.964 \pm .343$.

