1.2 Primary Study Endpoints

Part 1: The primary endpoint is completion of a standard PFT and an experimental rPFT during a single clinic appointment. At the endpoint, study outcomes will include:

- 1) The best forced vital capacity (FVC) and maximal inspiratory pressure (MIP) results from that visit's PFT
- 2) The best FVC and MIP results from that visit's rPFT
- 3) Survey responses from study participants.

Part 2: The primary endpoint for Aim 1 occurs at the clinic visit following initiation of NIV. At this time, participants will have had weekly measurements of FVC and MIP from self-administered rPFT procedures, as well as standard PFT assessments performed with the assistance of the respiratory therapist at approximately three-month intervals during standard in-person or telehealth clinic appointments. The primary endpoint for Aim 2 will be the change in self-efficacy scores from baseline. Changes will be compared across arms.

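### The 80% power in section 8.2 belongs to a simulated FVC contrast between monthly and quarterly testing groups, not to either Part 2 primary analysis

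*Combined protocol and SAP*

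**What the plan says.** Section 8.2 opens by setting size on feasibility: "Our sample size is predetermined based on our subjective ability to recruit patients". It then expects 75% of patients to reach the respiratory criteria for NIV, arrives at 15 per arm, and states "n=15, which provides 80% power to detect a difference in mean outcome between the two groups if the effect size is found to be 0.95".

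The effect size is supported by a simulation of 40 declining patients: "Half were sampled once every three months, and half were sampled every month". The outcome is FVC at the time NIV is recommended (47.0% against 43.4% predicted). The result is introduced by "The effect size of the difference in FVC between groups was" and is 0.964 ± 0.343.

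The Part 2 design is different. Section 1.1 says of the arms that "both perform weekly rPFT testing and one receives monthly NRHC". Section 7.1 adds the clinic tests: "For enrollees in both arms, standard FVC and MIP measurements obtained approximately every three months". The two primary outcomes are:

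- **Aim 1:** a time difference in days. The Figure 4 caption (7.2.2) runs it from first identified NIV need to the next standard clinic visit. Section 8.3 sets a 30-day criterion and names a two-sample rank-sum test.
- **Aim 2:** "The primary endpoint for Aim 2 will be the change in self-efficacy scores from baseline" (1.2), compared across arms. The hypothesis in 1.1 is that the coached teams "report higher self-efficacy in the respiratory management of the disease at 6 months". The analysis in 8.3 is a linear mixed model.

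No alpha or sidedness is given for any analysis. The nearest cue is the 95% confidence interval for the Aim 2 model in 8.3.

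**The concern.** A reader of 8.2 will take the two groups in the power sentence to be the two randomised arms, and will take the trial to have 80% power for what it randomises. Nothing in 8.2 supports that. The effect size comes from another outcome and from groups the trial does not form, and the 15 per arm is a count of threshold-crossers.

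What is at stake is interpretation. The only randomised comparison, Aim 2, has no stated detectable effect. If it came out null, the result could be reported as coming from a test with 80% power, which the plan never established.

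**Working it through.** **1. Reproduce the 80%.** The inputs from 8.2 are n = 15 per arm and d = 0.95. Alpha and sidedness are not stated, so 5% is assumed and both sides are tried. For a two-sample t-test the noncentrality is d × √(n/2) = 0.95 × √7.5 = 2.602, on 28 degrees of freedom.

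| Test | Critical t | t-test power | Rank-sum power (simulated, normal data) |
|---|---|---|---|
| One-sided 5% (same as two-sided 10%) | 1.701 | 81.4% | about 79% |
| Two-sided 5% | 2.048 | 70.9% | about 67% |

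The plan's figure reproduces at one-sided 5%. With the usual rank-sum efficiency of 3/π, the effective n is 15 × 0.955 = 14.3, and the effect detectable at 80% power, one-sided 5%, is 0.954. The 0.95 therefore looks like a detectable effect solved for a fixed n of 15, not an effect estimated for a trial outcome.

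**2. Where 15 comes from.** Section 8.1 aims for 40 completing pairs, which implies 20 per arm; 7.2.2 also counts 20 coached subjects. 0.75 × 20 = 15, the expected threshold-crossers per arm. Aim 2 is not restricted to crossers, and 7.2.2 keeps all procedures except rPFT going after NIV starts.

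**3. Where 0.964 comes from.** I re-ran the 8.2 simulation with its monthly decline of 3.5 (SD 3.4) and 20 per group. Three things were assumed: a baseline FVC of 82% predicted, independent monthly decrements and no measurement error. About 81% cross the threshold, mean FVC at crossing is 47.0 against 43.5, and the effect is about 0.95. The plan prints 80.6%, 47.0 against 43.4, and 0.964. Assumed baselines from 78 to 86 keep the effect between about 0.93 and 0.98. So 0.964 is well explained as an FVC contrast produced by testing frequency alone.

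**4. Set it beside the trial.**

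| | Simulation in 8.2 | Aim 1 | Aim 2 |
|---|---|---|---|
| Outcome | FVC at recommendation | Time difference in days | Change in self-efficacy |
| Contrast | Monthly v quarterly | Weekly v quarterly | Coached v not coached |
| Groups | Two independent groups | Both arms have weekly and quarterly tests | Two randomised arms |
| Number | 15 crossers per arm | Crossers | All with follow-up |

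**5. What Aim 2 could detect.** For a two-sample t-test at 80% power, solve for d with noncentrality d × √(n/2) on 2n − 2 degrees of freedom:

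| n per arm | Two-sided 5% | One-sided 5% |
|---|---|---|
| 20 | 0.91 | 0.80 |
| 25 | 0.81 | 0.71 |
| 30 | 0.74 | 0.65 |

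Twenty per arm is the completer target. Thirty (60/2) is a ceiling, because up to 60 teams enrol and randomisation follows only if the week-4 training check is passed. The range is needed because the Aim 2 hypothesis is at 6 months while participation lasts about a year, so the number with 6-month data may exceed the number completing.

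**The case against.** There are four fair replies.

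- **The 80% is correct under a reasonable choice.** The Part 2 hypotheses are directional, and one-sided 5% returns the figure. This stands. A reader might infer that the 80% is an error and that 71% is the true power. The documents do not support that: 71% needs a two-sided 5% test that they never declare, and the 95% interval in 8.3 belongs to the Aim 2 model, whereas 15 counts crossers, who matter to Aim 1.
- **The simulation is not foreign to the trial.** Aim 1 also asks about frequent against quarterly testing, and 8.3 names a two-sample test for it. This stands in part. The question is similar, but the endpoint (FVC, not days), the frequency (monthly, not weekly) and the independent groups all differ.
- **Size was set by feasibility, so power is immaterial.** Enrolment is indeed unaffected. But 8.2 still makes a power claim, and a trial sized by feasibility should say what it can detect.
- **Twenty per arm is not the only Aim 2 number.** This stands, and is why a range is given.

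**Conclusion.** The concern holds as a misattributed power statement. The 80% in 8.2 is a stated property of neither Part 2 primary analysis: its effect size is an FVC contrast between groups the trial does not have, and its n does not apply to Aim 2. Missing alpha and sidedness alone would be only missing detail, but here they move the same inputs between 81.4% and 70.9%.

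A reader might go on to infer that the trial is underpowered. The documents do not show that. They give no effect size or SD for self-efficacy or for the time difference, so power for either aim cannot be computed from them. With 20 per arm, an effect of 0.95 would have 83.3% power at two-sided 5%; what is missing is any reason to expect 0.95 for self-efficacy.

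The Aim 2 figures assume equal allocation and a two-sample approximation to the mixed model. The point should be fixed, but it is a correction to reporting, not to design.

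**What to change.** Change the text of 8.2 only:

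- Remove the 80% as a claim about the randomised arms.
- Keep the simulation as background, and label 0.95 and 0.964 as FVC-based figures for monthly against quarterly testing.
- Say that sample size is set by feasibility.
- State alpha and sidedness; the choice is the team's.
- For Aim 2, give the standardised between-arm difference in self-efficacy change detectable at 80% power, by a two-sample approximation: about 0.91, 0.81 and 0.74 at 20, 25 and 30 per arm (two-sided 5%), or 0.80, 0.71 and 0.65 (one-sided 5%). Keep the set that applies, and name 20 per arm as the completer target.
- For Aim 1, say only that no power is reported for the time difference in days. Do not describe it in 8.2 as within-patient or two-sample until the test in 8.3 and the Figure 4 definition have been reconciled.

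The cost is a less favourable stated figure and a commitment to an alpha and sidedness. Enrolment, visits and procedures do not change.
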